4.6.1.2 Derivation or calculation of outcome variable

TTP is defined as the time from randomisation to the time of the earliest objective disease progression (defined in Section 4.6.1.1), including death from any cause. Patients who have not progressed or died at the time of the data cut-off date or who have been lost to follow-up will be right-censored at the date of their last disease assessment.

For details of the primary statistical analysis of TTP see Section 6.4.1

4.6.2 Objective Response Rate (ORR)

4.6.2.1 Method of Assessment

Only patients with measurable disease at baseline, as per RECIST, will be assessed for objective response. The RECIST criteria will be used to perform the objective tumour assessments and best overall objective tumour response. **Tumour markers will not be utilised for this purpose** (see RECIST Criteria for details, Appendix C).

Categorization of the objective tumour response assessments will be based on the RECIST criteria for target and nontarget lesions. Response will be classified as complete response (CR), partial response (PR), stable disease (SD), or progressive disease (PD). In addition, a patient's best overall response will be determined from the start of treatment until progression.

For patients with an objective response of CR or PR, confirmations of response by repeat imaging must be performed at 4 weeks (or as soon as possible thereafter) following the date of response.

In the case of SD, follow-up measurements must have met the SD criteria at least once after study entry at a minimum interval of 8 weeks from the date of randomisation.

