3. STUDY PLAN AND PROCEDURES

3.1 Overall study design and flow chart

This Clinical Study Protocol has been subjected to a peer review according to AstraZeneca standard procedures.

This is a randomised, double-blind, parallel-group, multicentre, phase III study to compare two dose levels of fulvestrant. 720 postmenopausal women with oestrogen receptor positive advanced breast cancer who have either relapsed whilst on adjuvant endocrine therapy, or progressed whilst on first endocrine therapy for advanced disease, will be recruited.

Eligible patients will be randomised 1:1 to the following treatment groups:

- Fulvestrant 500 mg i.m. every 28 (\pm 3) days plus an additional 500 mg on day 14 (\pm 3) of first month only
- Fulvestrant 250 mg i.m. every 28 (\pm 3) days

Treatment will continue until disease progression, unless any of the criteria for treatment discontinuation are met first. If a patient progresses during the treatment period, the patient must be withdrawn from their randomised treatment and further treatment will be at the investigator's discretion.

All patients will be followed up for disease progression and survival, regardless of whether they have discontinued randomised treatment, unless they have withdrawn consent. Details of the first subsequent systemic breast cancer therapy received following discontinuation of randomised treatment (regimen and start and end date), as well as the best response to this therapy (according to the investigator's best judgment as per the RECIST criteria), will be collected.

There will be an Independent Data Monitoring Committee (IDMC) responsible for the review of safety data as detailed in Appendix D.

Following the primary analysis for TTP (and 50% survival analysis which was performed at the same time), all patients, regardless of whether they are still receiving randomised treatment, will enter the survival follow-up phase and be followed as per standard clinical practice. Patients remaining on randomised treatment will have their treatment unblinded and transferred to open label supplies. Patients who are currently receiving fulvestrant 250 mg, in consultation with their physician and the provision of re-consent to the open label follow-up phase of the study, will be given the option to be transferred to fulvestrant 500 mg.

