3.7 Pre-study, concomitant and post-study treatment(s)

All prior treatments for cancer and all drugs given to, or taken by, the patient at entry and during the study must be clearly documented on the appropriate CRF page.

The following treatment restrictions apply:

- Concomitant anticancer treatments are not permitted during the study. Such treatments are prohibited even if they are given for another indication (e.g. megestrol acetate for appetite stimulation, or methotrexate for rheumatological disorders).
- Radiotherapy may be given concomitantly for control of bone pain if therapy was started prior to randomisation. Patients requiring radiation for breast cancer or surgery for a breast cancer site after randomisation will be considered to have progressed, unless the investigator specified otherwise. If the investigator rules out progression, then irradiated or excised lesions will be considered non assessable for response and will be monitored only for disease progression.
- Chronic concomitant bisphosphonate therapy for hypercalcemia, and bisphosphonate treatment for the prevention of bone metastases are not permitted during the study. Bisphosphonate therapy for the treatment of osteoporosis is permitted during the study. Bisphosphonate therapy at the time of randomisation for the management of bone metastases is recommended as standard of care. If bisphosphonate therapy is initiated after randomisation the reason for its use must be clearly documented.
- Sex hormone containing drugs such as hormone-replacement therapy (HRT), progestational agents (megestrol acetate), DHEA, other androgens (e.g., oxandrolone) and SERMs (e.g. raloxifene (Evista)) are not permitted during the study. In rare cases where patients suffer severe menopausal symptoms, management with non-hormonal agents, e.g., clonidine or venlafaxine, is recommended. Use of an oestrogen-containing vaginal ring is allowed.
- In addition, other drugs than those mentioned above which may affect sex hormone status or disease response, such as systemic ketoconazole, systemic corticosteroids and adrenocortical suppressants are not allowed to begin after randomisation in to the study. However, the patient can continue to receive such drugs if they were taken before randomisation and the investigator is satisfied that the patient's hormonal status is stable.

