Details of the first subsequent systemic breast cancer therapy received following discontinuation of randomised treatment (regimen and start and end date), as well as the best response to this therapy (according to the investigator's best judgment as per the RECIST criteria), will be collected.

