Lesions must be assessed using the same method and technique on each occasion. Lesions will be recorded on the CRF page in the same order as they were recorded at screening. Details of any new lesions will also be collected. Response and progression will be calculated in comparison to the baseline tumour measurements obtained before starting treatment.

Tumour markers must not be used to assign progression or objective response (see RECIST, Appendix C).

Objective tumour response will be determined using a computer program, and these responses will be used in the summaries of TTP, ORR, CBR, DoR and DoCB. Bone only disease patients will only be included in the TTP summaries.

Baseline radiological tumour assessments should be performed no more than 4 weeks before the start of study treatment. Further tumour assessments will be made for all patients at all time points defined in the study plan (Table 1).

It is important to follow the assessment schedule as closely as possible because TTP is the primary variable and biases in analysis can occur if 1 treatment group is examined more often or sooner than the other. If an unscheduled radiological and clinical tumour assessment is performed, and the patient has not progressed, the next scheduled tumour assessment should still be performed at the planned time (as detailed in the study plan). This is in order to minimize any unintentional bias caused by some patients being monitored at a different frequency than other patients.

Patients who are withdrawn from study treatment for reasons other than disease progression will continue to have objective tumour assessments every 12 weeks until progression is documented. After progression, patients should be followed up for survival every 12 weeks as outlined in the study plan, unless the patient withdraws consent. Adherence to the study plan should be observed whenever possible.

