4.6.4.2 Derivation or calculation of outcome variable

CBR is defined as the proportion of all treated patients with measurable disease at baseline who have a best objective tumour response of CR, PR or SD \geq 24weeks.

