3.2.3 Evaluation of best overall response

The best overall response is the best response recorded from the start of treatment until disease progression/recurrence (taking as reference for progressive disease the smallest measurements recorded since the treatment started). In general, the patient's best response assignment will depend on the achievement of both measurement and confirmation criteria (see section 3.3.1). [Table 1](#) provides overall responses for all possible combinations of tumour responses in target and nontarget lesions with or without the appearance of new lesions.

(*Notes:*

- Patients with a global deterioration of health status requiring discontinuation of treatment without objective evidence of disease progression at that time should be classified as having "symptomatic deterioration." Every effort should be made to document the objective disease progression, even after discontinuation of treatment.
- Conditions that may define early progression, early death, and inevaluability are study specific and should be clearly defined in each protocol (depending on treatment duration and treatment periodicity).

- In some circumstances, it may be difficult to distinguish residual disease from normal tissue. When the evaluation of complete response depends on this determination, it is recommended that the residual lesion be investigated (fine-needle aspiration/biopsy) before confirming the complete response status).

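### Best overall response ends only at progression, so a response or 24-week stability first reached on a later systemic therapy counts for the randomised dose in ORR and CBR

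*Protocol*

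**What the plan says.** Section 4.6.2.1 fixes the response window: "a patient's best overall response will be determined from the start of treatment until progression". Appendix C 3.2.3 agrees: "The best overall response is the best response recorded from the start of treatment until disease progression/recurrence". CBR in Section 4.6.4.2 counts treated patients with measurable disease "who have a best objective tumour response of CR, PR or SD" lasting at least 24 weeks. ORR in Section 4.6.2.2 is built the same way from confirmed CR and PR.

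Section 3.3.5.1 lets patients stop treatment for reasons other than progression, including adverse events, their own choice and investigator discretion. Section 3.1 states: "All patients will be followed up for disease progression and survival, regardless of whether they have discontinued randomised treatment". Under Section 4.6, those who stop early "will continue to have objective tumour assessments every 12 weeks until progression is documented". The programmed responses from these scans feed ORR, CBR, DoR and DoCB.

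Section 3.7 arranges for collection of "Details of the first subsequent systemic breast cancer therapy received following discontinuation of randomised treatment", with start and end dates and the best response to it. No endpoint definition uses that start date. DoR and DoCB (Sections 4.6.6.2 and 4.6.5.2) end at progression or death and are censored only at data cut-off or loss to follow-up.

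**The concern.** ORR and CBR are meant to show the antitumour activity of the two doses, and Section 6.4 puts both under formal two-sided testing at 5%. Take a woman who stops fulvestrant at week 8 without progression, starts another systemic drug and has a PR at week 24 that is later confirmed. Under the stated window she is a responder for her randomised dose. The same PR is also recorded as her best response to the subsequent therapy, so one response is credited to two treatments. If she is merely stable past week 24 on the new drug, she counts as clinical benefit and enters DoCB.

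At stake is how ORR and CBR are read in each arm and, if pre-progression switching differs between arms, the comparison as well.

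**Working it through.** **1. The plan's own figure.** Only TTP is sized. Section 6.5 gives hazard ratio 0.8, two-sided 5%, 80% power and 632 events; allocation is 1:1 (Section 3.1). Schoenfeld: 4 × (1.960 + 0.842)² / (ln 0.8)² = 631. Freedman gives 636. Power with 632 events is 80.1%. The figure reproduces and does not depend on this point.

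**2. Can a post-switch scan count?** Reading the sections together:
- The window closes at progression only (4.6.2.1; Appendix C 3.2.3).
- Scans continue after early discontinuation (3.1, 3.3.5.2, 4.6).
- Subsequent therapy is recorded from discontinuation of randomised treatment, not from progression (3.1, 3.7).
- Section 3.7 prohibits concomitant anticancer treatment but attaches no analysis consequence.
- No section excludes scans taken after a new systemic therapy has started.

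So such a scan counts. For patients who switch only after progression, the window is already closed.

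**3. Size within an arm.** Let *f* be the share of measurable-disease patients who start another systemic drug before progression. Let *r* be the share of those who become a responder, or reach 24-week stability, only on that drug. The rate rises by *f* × *r*. The protocol gives neither quantity, so both are assumed: *f* from 2% to 10%, *r* from 10% to 40%. Shift in percentage points:

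| *f* | *r* = 10% | 20% | 30% | 40% |
|---|---|---|---|---|
| 2% | 0.2 | 0.4 | 0.6 | 0.8 |
| 5% | 0.5 | 1.0 | 1.5 | 2.0 |
| 10% | 1.0 | 2.0 | 3.0 | 4.0 |

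Section 3.2 gives earlier rates for fulvestrant of 19.2% (ORR) and 43.5% (CBR). With *f* = 5% and *r* = 20% they become 20.2% and 44.5%.

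**4. Size between arms.** With the same *r* in both arms, the spurious difference is (*f*₁ − *f*₂) × *r*.
- Equal *f*: 0 points.
- 10% against 5%, *r* = 20%: 2.0 − 1.0 = 1.0 point.
- 10% against 2%, *r* = 30%: 3.0 − 0.6 = 2.4 points.

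**5. Effect on the test, if the true rates are equal.** This uses a normal approximation with *n* = 360 per arm (720/2). That is an upper limit, because only measurable disease counts. For ORR and the 1.0-point case, the rates are 0.212 and 0.202. SE = √[(0.212 × 0.788 + 0.202 × 0.798)/360] = 0.0302, so *z* = 0.010/0.0302 = 0.331. The rejection probability is 1 − Φ(1.96 − 0.331) + Φ(−1.96 − 0.331) = 6.3%, against a nominal 5%. In the 2.4-point case it is 12.4%. With an assumed 250 per arm the two figures are 5.9% and 10.1%. For CBR with 360 per arm they are 5.8% and 9.9%.

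**The case against.** **ITT.** Section 6.3 applies the ITT approach by name to ORR, CBR, DoR and DoCB, so counting every scan until progression could be deliberate. It is deliberate and defensible for TTP and OS. But Section 6.3 settles who is analysed and in which arm. It does not settle which scans show activity of the randomised drug, and Sections 4.6.2.2 and 4.6.4.2 already limit the rates to treated patients with measurable disease.

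**SAP.** A response program's rules are usually set out in the SAP, which was not available for this review and may add a cut-off. However, the protocol does not leave the matter open: it names the end of the window itself. An added cut-off would change that stated window.

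**Narrow route.** Sections 3.1 and 3.3.5.2 mention further treatment at the investigator's discretion in connection with progression, and Section 3.7 bans concomitant anticancer drugs. This stands as a limit: only patients who stop and switch before progression matter, and they may be few. The documents do not exclude them.

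**Stronger readings.** A reader might infer any of the following, and the documents support none of them.
- *Poorer tolerability will show up as a higher response rate, or one dose is favoured.* No discontinuation or switching rate is given for either arm, and Section 3.2.1 expects no major safety concerns at the higher dose.
- *CBR must be inflated at least as much as ORR.* A patient with 24 weeks of stability on fulvestrant who then responds to a new drug raises ORR only.
- *Section 3.7 contradicts the response window.* It does say that "irradiated or excised lesions will be considered non assessable for response and will be monitored only for disease progression", but only where the investigator has ruled out progression. The default after new radiotherapy or surgery is to count the patient as progressed. The analogy shows that the protocol considered local treatment; it is not a direct contradiction.

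**Conclusion.** The point holds in a limited form. The stated window credits the randomised dose with a response or 24-week stability first reached on a subsequent systemic therapy. This affects the formally tested ORR and CBR, and entry to the descriptive DoR and DoCB. It concerns pre-progression switchers only.

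The inflation of about 0.2 to 4 points per arm rests wholly on the assumed switching and response rates. With equal switching and equal response to the new drug, the difference between arms is essentially unaffected. With unequal switching the bias could go either way, and the protocol does not show which. TTP, OS and the 632-event sample size are untouched. The change is worth making because the rule is explicit and the remedy is simple, not because a large bias has been shown.

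**What to change.** In Sections 4.6.2.1, 4.6.2.2 and 4.6.4.2, state that best overall response for ORR and CBR uses assessments up to the earlier of progression and the start of the first subsequent systemic breast cancer therapy. A patient without confirmed CR or PR by then is a non-responder. A patient without confirmed CR or PR, or stable disease of at least 24 weeks, by then has no clinical benefit. Both stay in the denominator. Add a line saying that this rule takes precedence over the window in Appendix C 3.2.3.

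DoR and DoCB then include only patients who qualify under this rule. Their descriptive end and censoring rules in Sections 4.6.6.2 and 4.6.5.2 can stay as written. Leave TTP and OS unchanged, and show the unrestricted ORR and CBR as a sensitivity analysis.

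The cost is a short text change and one date comparison in the response program; no new data are needed. Reported ORR and CBR become slightly lower, and a response seen on fulvestrant but confirmed only after the switch no longer counts. This edition describes the first survival analysis, done together with the primary analysis, in the past tense. If the rule is adopted after unblinding, the report should say so and give both sets of rates.

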4.6.2.2 Derivation or calculation of outcome variable

ORR is defined as the proportion of all treated patients with measurable disease at baseline who have a best objective tumour response of either CR or PR.

A best response of CR means that a response of CR is recorded at one visit and confirmed by repeat imaging at not less than 4 weeks later.

A best response of PR means that a response of PR is recorded at one visit and confirmed by repeat imaging at not less than 4 weeks later.

In the case of SD, follow-up measurements must have met the SD criteria at least once after study entry at a minimum interval of 8 weeks from the date of randomisation.

4.6.3 Overall Survival (OS)

4.6.3.1 Methods of assessment

After withdrawal from the study treatment, patients should be followed up for survival every 12 weeks, as outlined in the study plan, unless the patient withdraws consent.

4.6.3.2 Derivation or calculation of outcome variable

The overall survival (or time to death) is defined as the number of days from randomisation to death from any cause. Patients who are alive by the date of the data cut-off or who have been lost to follow-up will be right-censored in the analysis at their last contact date, that is, the date when the patient was last known to be alive.

4.6.4 Clinical Benefit Rate (CBR)

4.6.4.1 Methods of assessment

The RECIST criteria will be used to perform the objective tumour assessments and best overall objective tumour response. **Tumour markers will not be utilised for this purpose** (see RECIST Criteria for details, Appendix C).

4.6.4.2 Derivation or calculation of outcome variable

CBR is defined as the proportion of all treated patients with measurable disease at baseline who have a best objective tumour response of CR, PR or SD \geq 24weeks.

4.6.5 Duration of Clinical Benefit (DoCB)

4.6.5.1 Method of assessment

Duration of clinical benefit will be calculated for those patients with a best response of CR, PR or SD \geq 24 weeks.

4.6.5.2 Derivation or calculation of outcome variable

Duration of clinical benefit will be defined as from date of randomisation until the date of disease progression or death from any cause.

Any patient who has not progressed or died by the date of data cut-off, or who have been lost to follow up, will be right-censored in the analysis at the date of their last disease assessment

4.6.6 Duration of Response (DoR)

4.6.6.1 Methods of assessment

DoR will be calculated for those patients who have a best response of CR and PR based on RECIST criteria (Appendix C).

4.6.6.2 Derivation or calculation of outcome variables

Duration of response will be defined in two ways:

1. From date of first documentation of the response (CR or PR) until the date of disease progression or death from any cause.
2. From date of randomization until the date of disease progression or death from any cause.

Any patient who has not progressed or died by the date of data cut-off, or who have been lost to follow up, will be right-censored in the analysis at the date of their last disease assessment.

4.6.7 Translational research analyses

In patients with available tumour samples from either the primary tumour or a metastatic site (in the latter case the sample will have been obtained before treatment with the study drug), a molecular marker research will be carried out provided that the patient has given her written informed consent. The main aim of this sub-study will be the identification of a patient cohort which might derive the largest benefit from the use of the 500 mg dose of fulvestrant. In this context the evaluation of a panel of molecular markers involved in the HER pathway seems to be of interest because of the cross-talks existing between the ER and the HER pathway.

HER family receptors (EGF-R, HER-2, HER-3, HER-4), phosphorylated receptors, and downstream effectors such as pMAP Kinase and pAKT will be evaluated. In addition ER, PgR and Ki-67 will also be tested. The tumour samples will not be used for genetic testing.

Since this is a complex area of investigation, which is rapidly evolving and as yet not completely understood, data obtained in this study will not be definitive but potentially can be used in hypothesis generation.

Any data obtained from analysis of tumour tissue will be used for research only, and patient confidentiality will be preserved internally and in any presentations or publications. The samples will be available to scientists either within AstraZeneca or at laboratories/research

institutes contracted to AstraZeneca and/or the translational research coordinating centre and patient confidentiality will be preserved. Each patient will have a unique identifier called the patient E-code. A master list is retained at each centre linking initials to patient E-code.

It is not proposed that the analysis of results from a specific patient are made available routinely to either the subject of the treating physician, however, group results from this study will be published. The patient will be informed of this in the patient information sheet.

Samples will be retained for 10 years and data for 15 years in line with AstraZeneca's current policy.

